21.13.9 Biospecimen collection

21.13.9.1 Collection and shipping

21.13.9.1.1 Collection

All samples will be collected and processed as outlined below (also see lab manual)

Unstimulated 5-minute whole saliva collection: Each participant will split into a previously tared 50 mL conical tube, held on ice, every 30 seconds for 5 minutes; total saliva tube weight will be measured, and the sample will be processed immediately (centrifuged at 2800g for 5 mins at 4°C). Supernatant only will be aliquoted in 500-800 μ l increments and frozen at -80oC prior to shipping.

Oral microbiome swabs from dorsal tongue and buccal mucosa: a polyester swab will be rubbed on either the oral buccal mucosa (bilateral) or dorsal tongue for 30 seconds. The head of the swab will be cut off into a cryovial containing RNA later and will be held at room temperature until storage at -20oC prior to DNA extraction for analysis.

10 mL peripheral blood collection (CPT tube): Peripheral blood will be drawn into 2 CPT tubes. After collection, store tube upright at room temperature until centrifugation. Centrifuge at room temperature (18-25° C) in a horizontal rotor (swing-out head) for a minimum of 20 minutes (max 30 minutes) at 1500 to 1800 RCF (Relative Centrifugal Force) then prepare tubes for shipping. Blood samples should be centrifuged within 2 hours of blood collection for best results.

Biopsy of oral buccal mucosa, 4 mm punch: A 4 mm punch biopsy should be taken from affected area of oral buccal mucosal lining of cheek, ideally from an area with erythema and lichenoid lesion. Do not biopsy an ulcer, but tissue adjacent to an ulcer is fine. Deposit biopsy tissue into formalin and prepare for shipping.

Biopsy of labial minor salivary gland: An approximate 0.5 cm incision should be made in the labial mucosa, and 4-6 salivary glands lobules should be clipped out, deposited into formalin or saline, and then the site should be sutured closed. Deposit biopsy tissue into formalin if not already completed and prepare for shipping.

Biopsy of cutaneous skin, 4 mm punch: A 4 mm punch biopsy should be taken from affected area of cutaneous skin—generally from the most active area that will heal reasonably well. If skin is unaffected, biopsy should generally be taken from medial upper arm or torso. Face, hands, feet, and lower extremities should be avoided. If possible, the post-treatment biopsy should be done adjacent to the site of the pre-treatment biopsy. Deposit biopsy tissue into formalin and prepare for shipping.

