21.13.6 Introduction

21.13.6.1 Study objectives

21.13.6.1.1 Primary Objective

To characterize changes in the immune cellular profile before and after treatment with belumosudil with a focus on IL-17 production in the oral cavity

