21.13.6.1.3 Exploratory Objectives

To characterize changes in the skin immune cellular profile before and after treatment with belumosudil with a focus on IL-17 production.

To analyze and compare the effector cell profile of different sites (peripheral blood, skin, oral mucosa, minor salivary gland) during the pathogenesis of cGVHD.

To analyze changes in the local (saliva) and peripheral (blood) cytokine and chemokine profile after belumosudil treatment.

To compare changes in the oral microbiome before and after belumosudil treatment.

To analyze changes in the immune cell profile in peripheral blood before and after belumosudil treatment.

To compare gene expression profiles in immune cells before and after treatment with belumosudil in GVHD-affected tissues.

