21.13.10 Statistical section

To facilitate evaluation of the primary and other objectives, a control group will be included in the sample analyses. These control samples will be acquired only at the NIH from existing open protocols. The primary analysis group (i.e., Group 1, as described herein) will be the pre- and post-treatment samples from 20 evaluable participants treated with belumosudil on the ROCKstar study. Group 2 will be post-transplant (post-HSCT) control participants without cGVHD (PT cohort, n=10, single timepoint, must be 1-4 years out of transplant, with matched samples will be taken at a single visit). Group 3 will be healthy volunteers (HV Cohort, n = 5, age 30-65 years, collected only at the NIH under protocol NCT03602599 with matched samples, will be taken at a single visit).

The primary objective of this Companion Study is to characterize changes in the immune cellular profile before and after treatment with belumosudil with a focus on IL-17 production in the oral cavity. A total of 20 evaluable participants will have oral samples obtained both at pre-treatment and post-treatment; with 20 complete paired samples, a paired t-test will have 88.9% power to detect a difference in values between the two time points equal to 0.75 standard deviation of the

change (effect size = 0.75), based on a 0.05 two-sided significance level test. In practice, if the paired differences are not normally distributed ($p<0.05$ by a Shapiro-Wilks test), a Wilcoxon signed rank test will be used.

The secondary objective of this study, to determine feasibility of conducting a multi-center cGVHD study that includes analyses of tissue biopsies, saliva and peripheral blood, will be assessed by the estimate of the percentage of usable specimens which are obtained from the procedure. There is no fixed target, but the percentage of specimens which are usable will be reported along with a 95% confidence interval (CI). In addition, the fraction of participants in which both pre- and post-treatment oral samples are usable will be reported along with a 95% CI.

Although they are considered exploratory objectives, the sample sizes for the comparisons with controls will be assessed as follows:

The baseline IL-17-producing cells from the oral cavity identified at pre-treatment for participants who are to receive belumosudil will be compared to the number of cells obtained at a single time point from participants who do not have cGVHD.

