20 participants and 10 non-GVHD controls would have 87.6% power to detect an effect size of 1.25 (difference between the two groups equal to 1.25 SD of the values within each group) using a two-sample t-test with a 0.05 two-sided significance level. In practice, if the values within both groups are not normally distributed ($p<0.05$ by a Shapiro-Wilks test), a Wilcoxon rank sum test will be used.

The baseline IL-17-producing cells from the oral cavity identified at pre-treatment for participants who are to receive belumosudil will be compared to the number of cells obtained at a single time point from healthy volunteers; 20 participants with cGVHD and 5 healthy controls would have 81.9% power to detect an effect size of 1.5 (difference between the two groups equal to 1.5 SD of the values within each group) using a two-sample t-test with a 0.05 two-sided significance level. In practice, if the values within both groups are not normally distributed ($p<0.05$ by a Shapiro-Wilks test), a Wilcoxon rank sum test will be used.

All other evaluations will be considered completely exploratory and will be based on the available participants and usable data.

To allow for a small number of participants and controls which may not yield usable results for the primary analysis (or the main exploratory analyses involving the control participants), up to 24 participants with cGVHD, and 6 healthy volunteers may be enrolled.

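### Appendix M sets no post-treatment site for the buccal biopsy, which leaves the buccal part of the Companion Study's primary paired comparison open to outcome-dependent sampling

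*Protocol*

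**What the plan says.** The primary objective (Protocol 21.13.6.1.1) is: "To characterize changes in the immune cellular profile before and after treatment with belumosudil with a focus on IL-17 production in the oral cavity". The skin counterpart stands under the exploratory objectives (21.13.6.1.3): "To characterize changes in the skin immune cellular profile before and after treatment with belumosudil with a focus on IL-17 production".

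Buccal, labial gland and skin biopsies are all due at baseline and again at C7D1, or when treatment stops if that is earlier (21.13.7.2.1, 21.13.7.2.2, Table 8-1).

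Section 21.13.9.1.1 describes how each is taken:

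- **Buccal mucosa:** "A 4 mm punch biopsy should be taken from affected area of oral buccal mucosal lining of cheek, ideally from an area with erythema" and a lichenoid lesion. Ulcers are to be avoided, though tissue next to one is acceptable. The paragraph does not distinguish the two visits.
- **Skin:** an affected area, generally the most active one that will heal reasonably well, with named fallback sites if skin is unaffected. Then, qualified by an if-possible, "the post-treatment biopsy should be done adjacent to the site of the pre-treatment biopsy".
- **Labial gland:** an incision in the labial mucosa, with no requirement that the area be affected.

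The Statistical section (21.13.10) states: "A total of 20 evaluable participants will have oral samples obtained both at pre-treatment and post-treatment".

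**The concern.** A paired comparison assumes that the second measurement is taken on the same thing as the first, or at least on something chosen without regard to what happened in between. The buccal rule does not secure this. It tells the operator to look for affected tissue, and after six months of treatment the location of affected tissue is itself a result of treatment.

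In a partial responder, a literal reading passes over the healed baseline lesion and samples a patch that is still active. In a participant whose mouth has cleared, the instruction cannot be met and nothing replaces it, so the operator must improvise. With four centres and no common rule, practice may also differ between operators.

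What is at stake is the buccal contribution to the Companion Study's primary comparison. Section 21.13.9.3 uses immunohistochemistry on the biopsies to look for change in where IL-17-producing cells lie at effector sites, so the choice of site bears directly on the measurement. The main trial's ORR, safety analysis and alpha are not touched.

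**Working it through.** **1. The two site rules side by side (21.13.9.1.1)**

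| | Buccal (primary objective) | Skin (exploratory objective) |
|---|---|---|
| Which tissue | Affected, ideally erythema and lichenoid lesion | Affected, generally most active |
| Post-treatment site | Not stated | Adjacent to baseline site, if possible |
| Tissue not affected | Not stated | Named fallback sites |

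Both provisions missing for buccal tissue are present for skin, and Appendix M does not explain the difference.

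**2. Direction**

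If the second sample is taken from residual active mucosa, the measured change is lesion against remaining lesion. Improvement at the baseline site is not seen, and the gap is widest in those who improved most. That argues for a shift towards no change. If an operator biopsies cleared mucosa instead, this dilution does not arise.

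**3. The plan's own power figure**

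Inputs from 21.13.10: "with 20 complete paired samples, a paired t-test will have 88.9% power to detect a difference in values between the two time points"; "change (effect size = 0.75), based on a 0.05 two-sided significance level test".

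Paired t-test with n = 20, df = 19, two-sided 0.05. Power is the probability that a noncentral t variable with noncentrality d × √n falls outside the two-sided critical values.

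- d = 0.75: noncentrality 0.75 × √20 = 3.354, power 88.88%. This reproduces the stated 88.9%. (A normal approximation would give 91.8%.)

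**4. Illustration only**

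No figure in the documents says how much of the effect would be hidden. The attenuations below are assumptions, with n = 20 and the SD of the change held fixed.

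| Assumed share of 0.75 SD hidden | Effect (SD) | Noncentrality | Power |
|---|---|---|---|
| None | 0.75 | 3.354 | 88.9% |
| One tenth | 0.75 × 0.9 = 0.675 | 3.019 | 81.7% |
| One fifth | 0.75 × 0.8 = 0.60 | 2.683 | 72.1% |
| One third | 0.75 × 2/3 = 0.50 | 2.236 | 56.5% |

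If unmatched sites only added noise, a 20% larger SD of the change (also assumed) gives an effect of 0.75 / 1.2 = 0.625 SD and power 75.5%.

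**The case against.** **The text is silent, not wrong.** A reader might infer that the plan directs the second biopsy to whatever area is still affected. It does not say that. It gives one undifferentiated instruction, softened by advisory wording, and cites a lab manual that is not among the documents and may contain a post-treatment rule. This stands as a limit on the claim. Even so, the protocol states the matching rule for skin, and the primary tissue should have it in the same place.

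**Skin is not strictly matched either.** This is correct: the skin rule is adjacent, and only if possible. The contrast is between some rule and none.

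**The primary comparison is wider than the buccal punch.** Section 21.13.10 speaks of oral samples and does not name a specimen. Labial gland and saliva are also oral, are taken at both visits and are not chosen by lesion. The point must therefore be confined to the buccal part.

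**A cleared mouth need not lose the pair.** The biopsy is due at both visits whether or not a lesion is present, and cleared tissue would show improvement. The plan also allows for unusable samples ("up to 24 participants with cGVHD, and 6 healthy volunteers may be enrolled") and reports the fraction of usable pre/post pairs with a 95% CI. All of this is fair. What remains is that the site is undefined exactly where response was best.

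**Sampling affected tissue twice is a legitimate question.** The appendix does refer to effector sites and GVHD-affected tissues, and a residual lesion has also been exposed to the drug. But the stated objective is change from before to after treatment, and the plan does not present lesion-to-lesion sampling as a deliberate choice. A pathologist's reading of cGVHD status in the oral sections helps identify what was sampled, but not whether it came from the baseline site.

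**Matching has its own bias.** Returning to a site picked for activity, with no untreated cGVHD group, invites regression to the mean, away from no effect. This is a real downside. The plan already accepts it for skin, and selecting an active lesion at baseline happens under either rule.

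**Conclusion.** The point holds in a limited form. The buccal biopsy has a single lesion-directed site rule for both visits, with no return to the baseline site and no provision for cleared mucosa, although the exploratory skin biopsy has both. Followed as written, the buccal part of the primary paired comparison is open to outcome-dependent sampling, probably towards no effect.

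Two stronger readings are tempting and not supported. One is that the change in oral IL-17 is biased towards the null as a matter of fact. The direction is reasoned from the wording, depends on how sites act and on a lab manual not supplied, and does not extend to labial gland or saliva. The other is that the study's power is really 72% or 56%. The stated 88.9% is correct for its inputs; the lower figures show only what assumed losses of a fifth or a third of the effect would do. The true size is unknown.

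The consequence is confined to an optional biospecimen study of about 20 evaluable participants. A correction is still worthwhile because it concerns that study's primary comparison and is cheap.

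**What to change.** In 21.13.9.1.1, add to the buccal paragraph what the skin paragraph already has:

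- Record the location of the baseline buccal biopsy.
- If possible, take the post-treatment biopsy adjacent to that location whatever its current appearance, keeping the existing rule against biopsying an ulcer.
- Record lesion status at the biopsy site at both visits.
- Flag pairs where the site could not be matched, and repeat the paired comparison without them as a sensitivity analysis.

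The cost is a sentence or two in Appendix M and fields for location and lesion status, with no extra biopsy or visit. There are two downsides. Some post-treatment samples will be normal-looking mucosa with fewer cells to count. And regression to the mean at a site first chosen for activity remains possible; the recorded lesion status helps make it visible but does not remove it. The sample size and the power statement need no change.

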21.13.9.2 Sample Shipping

Biospecimens will be shipped to the NIH for further processing, storage and analysis. Samples should be shipped overnight via FedEx on Monday through Wednesday. Please notify lab below at time of shipping. Please make arrangements with lab if sample needs to be shipped Thursday or Friday and may arrive on the weekend.

Saliva aliquots may be stored at -80°C and shipped as a batch on dry ice.

All other samples: biopsies, blood and microbiome samples should be shipped at room temperature (not frozen) to the address below as soon as possible after collection
NIH, NIDCR, Oral Immunobiology Unit

ATTN: [REDACTED]

[REDACTED]

[REDACTED]

Office: [REDACTED]

Cell: [REDACTED]

Email: [REDACTED]

Note: CPT tubes containing separated blood cells must be placed in a red biohazard bag containing an absorbent material, such as a clinical pad. All glass has the potential for breakage; therefore, precautionary measures should be taken during handling. Please follow the instructions listed under “General Packaging Requirements” in the associated SOP document. Tubes for sample processing including cryovials with formalin for biopsies will be sent by the NIH lab to the collecting sites.

21.13.9.3 Correlative research studies

The following biospecimens will be collected and analyzed:

Saliva: Saliva will be processed and stored at -80°C until batched analyses are done using ELISA technology. Specific protein biomarkers of interest include IL-17A, IL-22, IL-21, IL-23, CCL20, IL-6, IL-17F, IL-1b, TNF, IL-26, CXCL10 and Zymogen Granule Protein 16B.

Microbiome swabs: Compositional and functional shifts in the oral microbiome will be assessed using targeted 16s sequencing or open-ended shotgun metagenomic sequencing approaches of non-human material only. Correlative laboratory assays may be done to corroborate initial findings.

Oral and skin biopsies: The oral tissue sections will be examined by a pathologist to assess oral cGVHD status. Fluorescent immunohistochemistry (IHC, 5+color) will be used to identify change in location and distribution of IL-17-producing cells at effector sites after belumosudil treatment. Correlative analysis of gene expression may be done using NanoString analysis on paraffin sections for interferon- and IL-17-related molecules.

Blood: Plasma will be used for multiplex ELISA analysis of IL-17-pathway chemokines and cytokines. Flow cytometric analysis may be done on fresh blood cells to identify phenotype, transcription factor expression and cytokine production.

21.13.9.3.1 Sample storage, tracking and disposition

The saliva, tissue and blood samples, collected for research will be stored by the Oral Immunobiology Unit (OIU), National Institute of Dental and Craniofacial Research (NIDCR), NIH. All data associated with archived clinical research samples is entered into a secure database. Access to this system is limited to OIU clinical staff, requiring individual login and password. All staff in the OIU laboratory complete training and maintain standards of computer security, as required locally.

The data recorded for each sample includes the deidentified (i.e., coded) participant ID number (as assigned by the ROCKstar study), trial name/protocol number, and date collected, as well as box and freezer location. All samples currently receive a unique bar code number, which is included in the OIU Stored Sample database. Only this bar code will be recorded on the sample vial and the vials will not be traceable back to the participants without authorized access to the Kadmon database.

Samples are stored in locked, monitored freezers at -80°C (saliva and blood) or -20°C (oral swabs) according to stability requirements. These freezers are located on site at the OIU Unit in Bethesda, MD.

Samples will not be sent outside NIH for analysis without appropriate Institutional Review Board (IRB) notification and an executed Material Transfer Agreement (MTA) if required.

All specimens obtained in the protocol will be used as defined in the protocol. Any specimens that are remaining at the completion of the protocol will be stored in the conditions described below. The study will remain open so long as sample or data analysis continues. Samples from consenting participants will be stored until they are no longer of scientific value or if a participant withdraws consent for their continued use, at which time they will be destroyed. The responsible site PI will report any loss or destruction of samples to the sponsor as soon as made aware of such loss.

If a participant withdraws consent, the associated data will be excluded from future sample distributions and analyses, but data already distributed for approved research use are not retrievable.

21.13.9.3.2 Data sharing plans

Participant's data will be deidentified and will be kept confidential. Participants will be identified by participant ID numbers in the clinical database. The link between the participants and their ID numbers will be securely maintained by the enrolling sites per local practices.

This study will comply with the NIH Public Access Policy, which ensures that the public has access to the published results of NIH funded research. It requires scientists to submit final peer-reviewed journal manuscripts that arise from NIH funds to the digital archive PubMed Central upon acceptance for publication.

The microbiome genomic data will be shared according to the NIH Genomic Data Sharing Policy: https://osp.od.nih.gov/wp-content/uploads/NIH_GDS_Policy.pdf.

This non-human data will be shared no later than the time of initial publication, per NIH policy: https://osp.od.nih.gov/wp-content/uploads/Supplemental_Info_GDS_Policy.pdf.

21.13.10 Statistical section

To facilitate evaluation of the primary and other objectives, a control group will be included in the sample analyses. These control samples will be acquired only at the NIH from existing open protocols. The primary analysis group (i.e., Group 1, as described herein) will be the pre- and post-treatment samples from 20 evaluable participants treated with belumosudil on the ROCKstar study. Group 2 will be post-transplant (post-HSCT) control participants without cGVHD (PT cohort, n=10, single timepoint, must be 1-4 years out of transplant, with matched samples will be taken at a single visit). Group 3 will be healthy volunteers (HV Cohort, n = 5, age 30-65 years, collected only at the NIH under protocol NCT03602599 with matched samples, will be taken at a single visit).

The primary objective of this Companion Study is to characterize changes in the immune cellular profile before and after treatment with belumosudil with a focus on IL-17 production in the oral cavity. A total of 20 evaluable participants will have oral samples obtained both at pre-treatment and post-treatment; with 20 complete paired samples, a paired t-test will have 88.9% power to detect a difference in values between the two time points equal to 0.75 standard deviation of the

change (effect size = 0.75), based on a 0.05 two-sided significance level test. In practice, if the paired differences are not normally distributed ($p<0.05$ by a Shapiro-Wilks test), a Wilcoxon signed rank test will be used.

The secondary objective of this study, to determine feasibility of conducting a multi-center cGVHD study that includes analyses of tissue biopsies, saliva and peripheral blood, will be assessed by the estimate of the percentage of usable specimens which are obtained from the procedure. There is no fixed target, but the percentage of specimens which are usable will be reported along with a 95% confidence interval (CI). In addition, the fraction of participants in which both pre- and post-treatment oral samples are usable will be reported along with a 95% CI.

Although they are considered exploratory objectives, the sample sizes for the comparisons with controls will be assessed as follows:

The baseline IL-17-producing cells from the oral cavity identified at pre-treatment for participants who are to receive belumosudil will be compared to the number of cells obtained at a single time point from participants who do not have cGVHD.

20 participants and 10 non-GVHD controls would have 87.6% power to detect an effect size of 1.25 (difference between the two groups equal to 1.25 SD of the values within each group) using a two-sample t-test with a 0.05 two-sided significance level. In practice, if the values within both groups are not normally distributed ($p<0.05$ by a Shapiro-Wilks test), a Wilcoxon rank sum test will be used.

The baseline IL-17-producing cells from the oral cavity identified at pre-treatment for participants who are to receive belumosudil will be compared to the number of cells obtained at a single time point from healthy volunteers; 20 participants with cGVHD and 5 healthy controls would have 81.9% power to detect an effect size of 1.5 (difference between the two groups equal to 1.5 SD of the values within each group) using a two-sample t-test with a 0.05 two-sided significance level. In practice, if the values within both groups are not normally distributed ($p<0.05$ by a Shapiro-Wilks test), a Wilcoxon rank sum test will be used.

All other evaluations will be considered completely exploratory and will be based on the available participants and usable data.

To allow for a small number of participants and controls which may not yield usable results for the primary analysis (or the main exploratory analyses involving the control participants), up to 24 participants with cGVHD, and 6 healthy volunteers may be enrolled.

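### Companion study: the Wilcoxon switch needs both groups to fail normality, so it rarely triggers with 5 controls; changing it to either group is nearly free

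*Protocol*

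**What the plan says.** Protocol 21.13.10 plans two comparisons of baseline IL-17-producing cells in the oral cavity. For the post-transplant controls it states that "20 participants and 10 non-GVHD controls would have 87.6% power to detect an effect size of 1.25", defined as a "difference between the two groups equal to 1.25 SD of the values within each group". For the healthy volunteers it states that "20 participants with cGVHD and 5 healthy controls would have 81.9% power to detect an effect size of 1.5", defined as a "difference between the two groups equal to 1.5 SD of the values within each group". Both figures are obtained "using a two-sample t-test with a 0.05 two-sided significance level".

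Each comparison then carries the same proviso. The t-test gives way "if the values within both groups are not normally distributed" (p<0.05 "by a Shapiro-Wilks test), a Wilcoxon rank sum test will be used").

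The section opens these comparisons with: "Although they are considered exploratory objectives, the sample sizes for the comparisons with controls will be assessed as follows". The primary companion analysis, 20 pre- and post-treatment pairs, has its own rule, which looks only at the paired differences. The SAP does not cover the companion comparisons, so this section is the only place where the rule is set.

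**The concern.** A normality check exists to move the analysis off the t-test when the data are clearly skewed. Read literally, a clear failure in the 20 cGVHD values is not enough here: the controls must fail as well. The switch can therefore never happen more often than the control group fails, and a sample of 5 or 10 seldom fails Shapiro-Wilk even when the underlying distribution is skewed.

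The endpoint is a cell count, which cannot be negative, so skew is plausible, although the documents give no distribution. What is at stake is the power that the Wilcoxon test could add, chiefly in the comparison with 5 healthy volunteers. There is also a risk that two analysts read the sentence differently and run different tests on the same data.

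**Working it through.** **1. The plan's own figures.** For an equal-variance two-sample t-test, the noncentrality is d × √(n₁n₂/(n₁+n₂)) with n₁+n₂−2 degrees of freedom.

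- 20 vs 10, d = 1.25: 1.25 × √(200/30) = 3.23, 28 df. Power is 87.60%.
- 20 vs 5, d = 1.5: 1.5 × √(100/25) = 3.00, 23 df. Power is 81.93%.

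Both stated figures reproduce.

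**2. How often the literal rule switches.** The groups are independent, so the chance that both fail is the product of the two failure rates. At log SD 1, simulated rates are:

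- 5 controls: cGVHD group 92.6%, controls 22.8%. Product 0.926 × 0.228 = 21.1%.
- 10 controls: cGVHD group 93.3%, controls 60.4%. Product 0.933 × 0.604 = 56.4%.

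With 5 controls, in about 93 − 22 = 71% of data sets the cGVHD values fail and the t-test is kept anyway. (The 22% allows for variation between runs.)

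**3. Power under the literal rule and under an either-group rule.** Inputs from the protocol: group sizes, two-sided 0.05, Shapiro-Wilk at 0.05, effect sizes. Assumptions: log-normal data, and the two effect models below. Each setting has 6,000 simulated data sets (standard error at most about 0.6 points), a pooled t-test and an exact Wilcoxon rank sum test.

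- *Additive*: shift of 1.5 SD (5 controls) or 1.25 SD (10 controls) of the values, as the plan defines the effect. The range covers shifts in either direction.
- *Multiplicative*: the same multiples, but of the log SD. This is not in the documents.

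| Controls | Log SD | Switch, literal rule | Additive: literal | Additive: either | Multiplicative: literal | Multiplicative: either |
|---|---|---|---|---|---|---|
| 5 | 0.5 | 5% | 82.0–83.5% | 83.3–88.8% | 64% | 75% |
| 5 | 0.75 | 13% | 84.8–87.6% | 88.2–95.7% | 46% | 74% |
| 5 | 1.0 | 21% | 87.8–91.1% | 93.0–98.3% | 32–33% | 75–76% |
| 5 | 1.5 | 38% | 93.9–96.6% | 98.5–99.9% | 30–31% | 76–77% |
| 10 | 0.5 | 12% | 88.7–89.4% | 91.3–94.7% | 82% | 86% |
| 10 | 0.75 | 35% | 92.1–93.9% | 95.7–98.5% | 78% | 86% |
| 10 | 1.0 | 56% | 94.7–96.8% | 97.8–99.6% | 75% | 85% |
| 10 | 1.5 | 82% | 98.3–99.2% | 99.5–100% | 75–76% | 85% |

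Repeat runs at log SD 0.5 and 1 differ by one to three points. For example, the literal rule with 5 controls, log SD 1 and a multiplicative effect gave 32–35%.

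**4. Normal data.** Literal against either: 81.3% vs 80.8% and 82.8% vs 82.4% (5 controls); 88.1% vs 88.0% and 88.3% vs 88.2% (10 controls).

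**5. Type I error.** About 4.0–6.1% over all settings under both rules.

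**The case against.** A reader might infer from the 32–35% that the stated 81.9% is lost under skewed data. The documents do not support that, because the two figures concern different effects. With log SD 1 and a 1.5 log-SD shift, the cGVHD SD is 9.69 against 2.16 in controls. The means are e² = 7.39 and e^0.5 = 1.65, a difference of 5.74. The pooled SD is √((19 × 9.69² + 4 × 2.16²)/23) = 8.85, so the effect is 5.74/8.85 = 0.65 SD, not 1.5. The 1.25 log-SD shift with 10 controls also comes to about 0.65 SD. Even with normal, equal-variance data a t-test at 0.65 SD has only 24% power (20 vs 5) or 37% (20 vs 10). At the effect the protocol does define, the literal rule stays at or above the stated power in every skewed setting tried. This objection stands in full.

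A reader might also infer that skewed data mostly go to the t-test with 10 controls as well. That is true for mild to moderate skew, but not at log SD 1, where Wilcoxon is already used in about 56% of data sets.

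The wording may have been meant as *not normal in both*, so that one failing group is enough. On that reading the rule is sound and only the sentence is unclear. That lowers the stakes, but it does not remove the need to settle the wording.

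Finally, skewness, its degree and a multiplicative effect are all assumptions, the comparisons are exploratory, and type I error is not at issue. All of that limits the weight of the point.

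**Conclusion.** The point holds as a cheap correction to an exploratory analysis. The literal condition works against its own purpose: with 5 controls and log SD 0.5 to 1 it switches in about 5–23% of data sets, and with 10 controls in about 12–57%. The power statements in 21.13.10 are right and need no correction for this reason.

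The practical loss depends on the form of the group difference. If it is additive, the literal rule forgoes only some extra power. If it is multiplicative, the loss against an either-group rule at log SD 0.5 to 1 is roughly 11 to 43 points with 5 controls (75 − 64; 75 − 32) and 4 to 10 points with 10 controls (86 − 82; 85 − 75). Even then the either-group rule does not reach 81.9% or 87.6%, and nor does Wilcoxon throughout (about 75–77% and 85–86%). These sizes rest on log-normal data; the documents offer nothing from which to choose the log SD.

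**What to change.** In Protocol 21.13.10, change *both groups* to *either group* in the two sentences on control comparisons, so that one Shapiro-Wilk failure moves the comparison to the Wilcoxon rank sum test. No sample size changes, and the paired analysis stays as it is.

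The cost with normal data is at most about half a point of power. Among the skewed settings, the only one in which the change cost more than that was exponential data with 5 controls and a shift in one direction (83.4% against 84.8%), still above the stated 81.9%.

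The alternative is to pre-specify Wilcoxon for both comparisons without a normality test. That is simpler, but the power must then be restated: with normal data it is about 86% (20 vs 10) and 76% (20 vs 5).
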